4.3.1.2 Other imputations

Partial dates

For imputation of the partial dates when not otherwise specified the following rule will apply: missing day is defaulted to the 15th of the month and missing month and day is defaulted to 01-Jan.

Incomplete lesion assessment dates

All investigation dates (e.g. MRI scan, CT scan) must be completed with day, month and year. If one or more assessment dates are incomplete but other investigation dates are available, this/these incomplete date(s) are not considered for calculation of the assessment date and assessment date is calculated as the earliest date of all investigation dates at that evaluation number. If all measurement dates have no day recorded, the 1st of the month is used. If the

month is not completed, for any of the investigations, the respective assessment will be considered to be at the date which is exactly between previous and following assessment. If a previous and following assessment is not available, this assessment will not be used for any calculation.

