3.2 Analysis population(s)

The **full study population** will include all patients that satisfy the study inclusion criteria. This population set will be used for all secondary [REDACTED] efficacy analyses and for safety analyses.

The **efficacy population** is a subset of the full study population, which will be used for the analysis of the primary endpoint and includes patients who meet the following criteria:

- Patient had at least one target lesion
- Patient had an imaging scan performed on the index date (or up to 24 weeks prior to the index date) for at least one target lesion

3.3 Key post index date time points for reporting endpoint over time.

Considering the retrospective nature of the study, patients might have data available at different time-points. In order to maximize the use of data abstracted, key time points and associated time windows are identified for reporting purpose. For each of these time-points or intervals all patients with data available will be used. The total number of patients in a time interval will be equal to the number of patients with at least one valid assessment in that specific time window. The number of patients (N) in each interval will be summarized in the disposition table and used throughout the report. Only the time points with data available for at least 10% of the patients will be displayed in the corresponding output.

Key study time points are summarized in [Table 3-1](#).

Table 3-1 Time windows for post-index date key-time point

Key time-points	Allowed windows
4 weeks	Up to 10 weeks
12 weeks	[10 to 20 weeks[
24 weeks*	[20 to 32 weeks[
36 weeks	[32 to 40 weeks[
52 weeks	[40 to 58 weeks[
End of study	4 weeks prior to and up to min(study treatment discontinuation + 30 days, cut-off date)

* 24 weeks or 6 months (+/- 4 weeks).

After week 52 intervals of approximately 11 weeks (e.g. 63 weeks, 74 weeks, etc.) with a time window of +/- 5 weeks will be used until the "end of study".

Week 24 windows (+/- 4 weeks) is intended to include assessments performed 24 weeks or 6 months after index date, where 6 months is approximated to week 27.

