The last interval, referred to as "end of study" in [Table 3-1](#), will include data available within the last 4 weeks prior to study treatment discontinuation plus 30 days or cut-off date, whichever comes first. When a patient discontinues data will be reported in the "end of study" time window as well as the one corresponding to the assessment (e.g., a patient discontinued treatment at week 58 data will be reported in the key point 52 weeks interval and in the "end of study").

In instances where more than one measure is reported in the time window associated with a key time-point (e.g., at 12 weeks), the measurement taken closest to the key-time point will be considered in the analysis. If two measures were taken on dates that are equidistant from the key time-point (e.g., 12 weeks - 5 days and 12 weeks + 5 days following the index date), the measure associated with a more severe condition (e.g., larger non-target lesion volume, higher pain severity score, lower functional assessment score) will be considered.

In instances where both a non-missing value and a missing or unknown value are reported in the time window associated with a key time-point, only the non-missing value will be considered in the analysis.

Similar rules applies to the volumetric measurement available for the patients.

If a patient has more than one volumetric measurement available for a single target lesion in the time window associated with the index date (i.e., up to 24 weeks prior to the index date) or at 24 weeks (i.e., ± 4 weeks) following the index date, the measurement taken closest to the index date or 24 weeks following the index date will be considered in the analysis. If two volumetric measurements for a single target lesion were taken on dates that are equidistant from the index date or 24 weeks following the index date, the larger of the two measurements (i.e., greatest volume) will be considered. All measurements available will be listed.

Imputation rules for the dates are reported in the [Appendix](#).

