4.1 General definitions

Study treatment

The term study treatment or study drug will be used in this document and will refer to alpelisib.

Date of first administration of study drug

The date of first administration of alpelisib is defined as the first date when a non-zero dose of alpelisib is administered and recorded in the (e)CRF. This date is referred to as index date and used as reference start date.

Date of last administration of study drug

The date of last administration of alpelisib is defined as is the last date when a nonzero dose of alpelisib is administered and recorded in the (e)CRF.

Study day

The study day, describes the day of the event or assessment date, relative to the reference start date. The study day is defined as:

- The date of the event (visit date, onset date of an event, assessment date etc.) – reference start date + 1 if event is on or after the reference start date;
- The date of the event (visit date, onset date of an event, assessment date etc.) – reference start date if event precedes the reference start date.

Time unit

A year length is defined as 365.25 days. A month length is 30.4375 days (365.25/12). If duration is reported in months, duration in days will be divided by 30.4375. If duration is reported in years, duration in days will be divided by 365.25.

Baseline

For safety and efficacy evaluations, the last available assessment on or before the date of start of alpelisib is defined as “baseline” assessment.

On-treatment assessment/event and observation periods

For adverse event reporting the overall observation period will be divided into two mutually exclusive segments:

1. *pre-index date/pre-treatment period*: from up to 24 weeks prior to the index date through to the day prior to the index date.
2. *post-index date/on-treatment period*: from date of first administration of study treatment to 30 days after date of last administration of alpelisib (including start and stop date).

Safety summaries (tables, figures) include only data from the on-treatment period with the exception of baseline data which will also be summarized where appropriate (e.g. change from baseline summaries).

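### Incompletely dated lesion scans are assigned dates with no check against first dose, so the date rule can decide which scan serves as baseline or Week 24 for the primary endpoint

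*SAP*

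**What the plan says.** The paragraph on incomplete lesion assessment dates in SAP 4.3.1.2 starts with a requirement: "All investigation dates (e.g. MRI scan, CT scan) must be completed with day, month and year". It then provides for the cases where this fails:

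- Another investigation at the same evaluation has a usable date: "this/these incomplete date(s) are not considered for calculation of the assessment date".
- No investigation has a day: "If all measurement dates have no day recorded, the 1st of the month is used".
- The month is missing: "the respective assessment will be considered to be at the date which is exactly between previous and following assessment".
- The month is missing and there are no neighbours: "If a previous and following assessment is not available, this assessment will not be used for any calculation".

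These dates decide which scans enter the primary endpoint. SAP 4.1 takes "the last available assessment on or before the date of start of alpelisib is defined as" baseline. SAP 3.2 admits a patient to the efficacy population only with a scan of a target lesion at index or in the 24 weeks before. SAP Table 3-1 sets the Week 24 window at [20, 32) weeks. When several scans qualify, SAP 3.3 says that "the measurement taken closest to the index date or 24 weeks following the index date will be considered in the analysis".

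SAP Table 4-3 handles partial dates for other assessments. For a date in the month of treatment start it takes the later of treatment start and the 15th. Its title covers laboratory tests, vital signs, ECG, surgery, questionnaires and others, but not imaging.

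**The concern.** The response compares two scans, and both are chosen by date. Protocol 6.9 acknowledges that clinical practice has no common assessment schedule, so the date of a neighbouring scan says little about when an undated one was taken. The midpoint rule as written also makes no use of a recorded year.

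Two things follow:

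- A scan taken after first dose can be dated as pre-treatment. It can then serve as baseline, or bring into the efficacy population a patient who has no true pre-treatment scan.
- A scan of unknown timing can fill the Week 24 window. Under SAP 3.5.1 this turns a missing response into an observed one and changes the complete-case denominator.

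Sensitivity Analyses 1 and 2 in SAP 3.5.3 deal only with missing responses. A scan with an imputed date counts as observed, so neither analysis tests it.

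**Working it through.** The plan states no figure here, so there is none to reproduce. The rules were applied as written. Every percentage assumes uniform true dates, which the documents do not state.

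**1. Day missing, scan in the index month.** The imputed day is 1, and the index day is at least 1, so the imputed date is on or before index in 100% of cases. For a month of D days, with scan and index days uniform and independent:

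P(scan truly after index) = (D − 1)/(2D); for D = 30, 29/60 = 0.483.

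Enumerating all day pairs for 2016–2019 gives 0.484, with a backward shift of up to 30 days. Over index dates from 1 January 2016 (assumed start) to 23 September 2019, a day-missing scan is dated on or before index with this frequency:

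| True days after first dose | Dated on or before index |
|---|---|
| 7 | 77% |
| 14 | 54% |
| 28 | 8% |

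If the treatment start day is also missing, SAP 4.3.1 sets it to the 15th, and a same-month scan on the 1st always precedes it.

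**2. Effect of an on-treatment baseline (illustrative volumes).** True baseline 100, early on-treatment scan 90, Week 24 scan 78:

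- From the true baseline: (78 − 100)/100 = −22.0%, which meets the 20% threshold.
- From the on-treatment scan: (78 − 90)/90 = −13.3%, which does not.

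**3. Month missing, Week 24.** With the previous scan b weeks before index and the next scan f weeks after, the midpoint is (f − b)/2. It lies in [20, 32) when 40 ≤ f − b < 64. For b = 0:

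| Next scan f (weeks) | Midpoint (weeks) | In Week 24 window |
|---|---|---|
| 32 to <40 | 16 to <20 | never |
| 40 to <58 | 20 to <29 | always |

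In the first row, a scan truly taken in Week 24 is moved out. In the second, the chance that the true date is in the window is 12/48 = 25% for f = 48 and 12/52 = 23% for f = 52.

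**4. Month missing, baseline.** Neighbours at weeks −24 and +20 give (20 − 24)/2 = −2 weeks, which is a baseline date. Yet 20/44 = 45% of that interval is on treatment.

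**5. Day missing, Week 24.** The window is days 140 to 223. A scan as late as day 223 + 30 = 253 (36.1 weeks) can be moved in. A scan as late as day 139 + 30 = 169 (24.1 weeks) can be moved out. With true days 1–364 and the index dates of step 1, about 17.5% of scans dated into the window are truly outside it, and about 17.5% of true window scans are moved out.

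**6. Scale.** Protocol 6.6 plans on 50 patients, so one changed response is 1/50 = 2 percentage points. For example, 20/50 = 40.0% (Clopper-Pearson 26.4–54.8%) becomes 21/50 = 42.0% (28.2–56.8%). A missing response that becomes an observed responder gives 21/51 = 41.2% (27.6–55.8%).

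**The case against.** The strongest reply is that the rules may never be used. The SAP requires complete dates and ignores an incomplete one when another is available at the same evaluation. It drops a month-missing scan that has no neighbours. Scans go to a central imaging vendor, and Protocol 6.10 provides for entry checks and site queries. Further detail sits in the Independent Central Review Charter, which is not among the documents. All this stands and limits the likely size. It does not make the rules correct when they are used, and the SAP evidently foresaw that they might be.

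A second reply is that target lesions are selected from pre-index images before any later image is assessed. That protects the choice of lesions. It does not stop a later scan, once given an early date, from supplying the baseline volume.

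A third is that an on-treatment baseline would tend to understate shrinkage and so is conservative. That is fair for that part, but it remains measurement error in the primary endpoint, and it does not apply to the Week 24 part.

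A reader might infer that the SAP singles out lesion scans for early dating. It does not. Tables 4-1 and 4-3 also use the 1st for months after the index month, and the general rule in 4.3.1.2 sends a missing month and day to 1 January. The real contrast is confined to the index month, where Table 4-3 has a check against treatment start and scans have none.

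**Conclusion.** The point holds as a defect in a stated rule. Day-missing scans in the index month always become candidates for baseline, and a month-missing scan can be placed in or out of the Week 24 window regardless of its true date. An on-treatment scan actually serves as baseline only if no true pre-index scan is closer to index.

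Two stronger readings are tempting. One is that the midpoint rule puts undated scans into Week 24 as a matter of course. The 100% result belongs to one configuration, and a slightly earlier next scan gives 0%. The other is that the response rate is inflated. The direction is not fixed: the baseline error tends to lower response, and the Week 24 error can go either way.

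The number of incomplete scan dates is not stated, so the effect on the result may be small or nil. If any patient is affected, each changed response is worth about 2 points at the planning size of 50, and more if the complete-case set is smaller.

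**What to change.** Amend SAP 4.3.1.2 as follows:

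1. Query the site or the imaging vendor for the acquisition date of any scan with an incomplete date.
2. If the date stays incomplete, use the scan for baseline or Week 24 only when every date compatible with the recorded part falls in that window and on the same side of index. A month-only scan whose whole month lies inside the window is kept.
3. Otherwise list the scan and treat that volume as not assessed. The resulting missing response is then covered by Sensitivity Analyses 1 and 2. It should not fall under the separate clause that makes a patient a non-responder when a Week 24 volume cannot be calculated.
4. Do not use the midpoint rule for baseline or Week 24.

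Extending the Table 4-3 rule to scans would not be enough. With an index day of the 15th or later, the imputed date equals the index date and still counts as on or before it. Under uniform days this leaves about 28% of truly on-treatment same-month scans eligible as baseline.

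The cost is a few lines of SAP text and a date query. The downside is possibly some additional missing responses, or the loss from the efficacy population of a patient whose only baseline scan cannot be dated. The documents give no basis for a number.

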4.4 Laboratory parameters derivations

Grade categorization of lab values will be assigned programmatically as per NCI Common Terminology Criteria for Adverse Events (CTCAE) version v4.03. The calculation of CTCAE grades will be based on the observed laboratory values only, clinical assessments will not be taken into account. The criteria to assign CTCAE grades are given in Novartis internal criteria for CTCAE grading of laboratory parameters. The latest available version of the document based on the underlying CTCAE version v4.03 at the time of analysis will be used. For laboratory tests where grades are not defined by CTCAE v4.03, results will be graded by the low/normal/high (or other project-specific ranges, if more suitable) classifications based on laboratory normal ranges.

A severity grade of 0 will be assigned for all non-missing lab values not graded as 1 or higher. Grade 5 will not be used. For laboratory tests that are graded for both low and high values, summaries will be done separately and labelled by direction, e.g., sodium will be summarized as hyponatremia and hypernatremia.

Imputation Rules

CTC grading for blood differentials is based on absolute values. However, this data may not be reported as absolute counts but rather as percentage of WBC.

If laboratory values are provided as '<X' (i.e. below limit of detection) or '>X', prior to conversion of laboratory values to SI unit, these numeric values are set to X.

The following rules will be applied to derive the WBC differential counts when only percentages are available for a xxx differential

$$\text{xxx count} = (\text{WBC count}) * (\text{xxx \%value} / 100)$$

Further derivation of laboratory parameters might be required for CTCAE grading. For instance, corrected calcium can be derived using the reported total calcium value and albumin at the same assessment using the following formula:

$$\text{Corrected Calcium (mg/dL)} = \text{Calcium (mg/dL)} - 0.8 [\text{Albumin (g/dL)} - 4]$$

In order to apply the above formula, albumin values in g/L will be converted to g/dL by multiplying by 0.1, calcium values in mmol/L will be converted to mg/dL by dividing by 0.2495. For calculation of laboratory CTC grades 0 and 1, the normal range for derived corrected calcium is set to the same limits (in mg/dL) as for calcium.

CTC grades for the derived absolute WBC differential counts (neutrophils, lymphocytes) and corrected calcium will be assigned as described above for grading

